7.2.4 Switching Phase – Visit 2 (Day 21 ± 7 days)

The following procedures will be completed in a private clinic space in the Clinical Research Center. Participants and researchers will be wearing appropriate PPE at all times, except for noted measures where the participant will need to remove their mask (when COVID protocols apply).

Prior to the visit:

7.2.4.1 Participants will then be provided with instructions to complete measures via a home computer/smart phone (see table of measures). A link to the surveys in REDCap will be sent to the participant's email address or phone the day of the clinic visit. Participants will be instructed to complete all questionnaires within 24 hours. Participants unable to complete the questionnaires at home via a computer/smart phone will be called by the researchers to complete the questionnaires.

(Part A): Participant Check-In

7.2.4.2 The following measures will be completed:

- **7.2.4.2.1** Adverse events will be documented, and any concomitant medication changes will be recorded.
- **7.2.4.2.2** The cigarette and study product use diary will be collected by the researcher and entered into Daily Cigarette and E-cig Use Diary Log in Redcap.
- **7.2.4.2.3** Use of other tobacco products in the past 7 days will be assessed via the Other Tobacco Use form.
- **7.2.4.2.4** Participants will be encouraged to remain abstinent from cigarettes.
- **7.2.4.2.5** Participants will be instructed to complete daily diaries related to their study product and cigarette use (E-cigarette Daily Diary). They will also be asked to return all used and unused e-cig pods at their next study visit.
- **7.2.4.2.6** Participants will be provided with a supply of pods based on their usage.

(Part B): Completion of Biomeasures

- **7.2.4.3** The participant will then leave the clinic space to have their blood pressure and weight measured.
- **7.2.4.4** Participants will then be taken to the CRC bathroom and will be asked to provide a urine sample.
 - 7.2.4.4.1 A pregnancy test will be completed for women of childbearing potential.
 - **7.2.4.4.2** Participants will complete an exhaled carbon monoxide reading.
 - 7.2.4.4.3 Pulmonary Function Testing (PFTs) PFTs will be conducted as described in the Time and Events Table at Visits 1, 2, and 3. Any significant worsening (10% worsening or greater) in pulmonary function will be documented as an adverse event. All adverse events will be documented and reviewed by the Medical Monitor within 5 business days. In cases where the medical monitor suspects that a participant may be having a respiratory adverse event related to the study, a pulmonologist ([name]) will be consulted. The pulmonologist will make any needed medical recommendations and a

determination regarding whether the participant is able to continue with the study.

7.2.4.4.3.1 When COVID protocols apply: The researcher will then leave the clinic space to complete the CO and pulmonary function test, as the participant will need to remove their mask for this test. This will be facilitated by a two-way mirror and an intercom system. The researcher will remain outside of the clinic space for 15 minutes following the completion of this test and will use a timer to ensure that this time restriction is met.

(Part C): Visit Wrap-Up

- 7.2.4.5 As participants are leaving the clinic space, they will be provided with new pods. Based on usage information collected during the past two weeks' phone calls, participants will be provided with a new supply of SREC pods as needed. Participants will be able to retain their unused pods from the previous visit.
- **7.2.4.6** Once participants complete the additional questionnaires (completed at home within 24 hours), they will be compensated for the visit. The funds will be automatically loaded onto the card.
 - **7.2.4.6.1** Those who do not complete the visit by completing the at-home questionnaires (which includes an option to opt-out of answering) will only be compensated for travel.
- 7.2.5 Switching Phase Phone Contact #3 (Day 28 ±7 days) and Phone Contact #4 (Day 35 ± 7 days) During each phone contact, daily study product and cigarette use will be collected, adverse events or changes to concomitant medications will be documented, and participants will be asked to verbally answer the measures indicated in the Time and Events Table during the phone call. Participants' answers will be entered directly into REDCap by the researcher at the time of the call. Participants will also be provided with advice/encouragement to remain abstinent from cigarettes. Participant's compensation for completing the phone call will be added to their Greenphire ClinCard.

7.2.6 Switching Phase – Visit 3 (Day 42 -7/+14 days)

The following procedures will be completed in a private clinic space in the Clinical Research Center. Participants and researchers will be wearing appropriate PPE at all times, except for noted measures where the participant will need to remove their mask (when COVID protocols apply).

Prior to the visit:

7.2.6.1 Participants will be provided with instructions to complete measures via a home computer/smart phone (see table of measures). A link to the surveys in REDCap will be sent to the participant's email address or phone the day of the clinic visit. Participants will be instructed to complete all questionnaires within 24 hours. Participants unable to complete the questionnaires at home via a computer/smart phone will be called by the researchers to complete the questionnaires.

(Part A): Participant Check-In

- **7.2.6.2** The following measures will be completed:
 - **7.2.6.2.1** Adverse events will be documented, and any concomitant medication changes will be recorded.

- **7.2.6.2.2** The cigarette and study product use diaries will be collected by the researcher and entered into the Daily Cigarette and E-cig Use Diary Log in Redcap. Participants will stop using the diaries at this point of the study forward.
- **7.2.6.2.3** Use of other tobacco will be assessed via the Other Tobacco Use form.
- **7.2.6.2.4** All used and unused e-cig pods will be collected by the researcher for review. Participants will then be able to retain some of the unused pods based on their usage.
- **7.2.6.2.5** Participants will be encouraged to remain abstinent from cigarettes.
- **7.2.6.2.6** Participants will also verbally be provided with information regarding how they can purchase their own e-cig devices and products, similar to the one used in the study. Participants will be instructed to purchase e-liquid from reputable companies and to not buy from unknown or illicit sources.

(Part B): Completion of Biomeasures

- **7.2.6.3** The participant will then leave the clinic space to have their blood pressure and weight measured.
- **7.2.6.4** Participants will then be taken to the CRC bathroom and will be asked to provide a urine sample.
 - **7.2.6.4.1** A pregnancy test for women of child-bearing age will be completed.
- **7.2.6.5** The participants will return to the clinic space to completed the 10 minute Holter EKG.
- 7.2.6.6 Participants will complete an exhaled carbon monoxide reading.
- 7.2.6.7 Pulmonary Function Testing (PFTs) PFTs will be conducted as described in the Time and Events Table at Visits 1, 2, and 3. Any significant worsening (10% worsening or greater) in pulmonary function will be documented as an adverse event. All adverse events will be documented and reviewed by the Medical Monitor within 5 business days. In cases where the medical monitor suspects that a participant may be having a respiratory adverse event related to the study, a pulmonologist ([name]) will be consulted. The pulmonologist will make any needed medical recommendations and a determination regarding whether the participant is able to continue with the study.
 - **7.2.6.7.1** When COVID protocols apply: The researcher will then leave the clinic space to complete the CO and pulmonary function test, as the participant will need to remove their mask for this test. This will be facilitated by a two-way mirror and an intercom system. The researcher will remain outside of the clinic space for 15 minutes following the completion of this test and use a timer to ensure that the time restriction is met.

(Part C): Visit Wrap-Up

- **7.2.6.8** Once participants complete the additional questionnaires (completed at home within 24 hours), they will be compensated for the visit. The funds will be automatically loaded onto the card.
 - **7.2.6.8.1** Those who do not complete the visit by completing the at-home questionnaires (which includes an option to opt-out of answering) will only be compensated for travel.

7.2.7 Follow-Up Phase – Phone Contact #5 (Day 70 ± 7 days)

During this follow-up phone contact, past 7 day study product and cigarette use will be collected via a 7 day timeline follow-back (TLFB) procedure (meaning that participants will be asked to recall their use from memory for the past 7 days), adverse events or changes to concomitant

medications will be documented, and participants will be asked to answer the measures indicated in the Time and Events Table.

7.2.8 Follow-up Phase – Interview Visit 4 (Day 70 + 60 days) (Optional study visit)

At consent, participants will be given the option to be considered to participate in an additional study procedure, a structured interview about their experiences using the e-cig device to stop smoking.

Participants who consent to the optional part of the study will be contacted by the researchers after completion of the study (after Visit Ph #5) to schedule an additional study visit to complete the interview. Only participants who complete the study (ie. Complete Ph #5) will be contacted.

Participants who are contacted and who agree to participate in the interview will be contacted to schedule an in-person visit at the study center. The interview will take place via ZOOM and will last approximately 30-60 minutes. Interview questions will be related to the participant's experience using the e-cig and attempting to switch completely from cigarettes. All interviews will be recorded and transcribed. In addition, participants will be asked to provide their past 7 day cigarette (via 7 day TLFB) and e-cigarette use.

- We plan to recruit 40 participants to complete the interview part of the study. We plan to recruit participants who met the following criteria:
- 8 participants who successfully switched and were randomized to the Omg/ml group
- 12 participants who successfully switched and were randomized to the 58mg/ml group
- 8 participants who did not successfully switch and were randomized to the Omg/ml group
- 12 participants who did not successfully switch and were randomized to the 58mg/ml group

Successfully switching for the interview part of the study will be defined by no cigarette use reported in the past 7 days reported at Visit 3 and Visit Ph #5 and a CO < 6ppm at Visit 3.

The first participants who meet the outlined criteria will be contacted by the researchers. We will continue to recruit participants for each category until all interviews for that category is completed. The interviews will be completed by blinded researchers but the management of the recruitment of participants for the interview will be managed by an unblinded study team member. This will ensure that recruitment for each category is correctly executed.

7.2.9 Follow-up Phase – Product Use Visit (Day 70 + 60 days) (Optional study visit)

At consent, participants will be given the option to be considered to participate in an additional study procedure. Participants who consent to the optional part of the study will be contacted by the researchers after completion of the study (after Visit Ph #5) to schedule the additional visit.

Participants who meet the following criteria will be contacted:

- Complete the study (ie. Complete Ph #5)
- Still using a nicotine containing product at Ph #5

The first participants who meet the outlined criteria will be contacted by the researchers. We will continue to recruit participants this optional visit until 10 participants have completed.

For the procedure, participants will be asked to use the SREC product in the lab while blood is collected. First, participants will be asked to abstain from any nicotine containing products for at least 14 hours before attending the visit. Once they arrive at the study center, a CO will be collected to verify abstinence (CO < 15 ppm to be eligible). Then, participants will complete

baseline questionnaires about withdrawal and craving. Then, participants will be given the SREC device with a 5% pod to use in the lab in a standard manner of 1 puff every 20 seconds for 14 puffs total (4 minutes, 20 seconds). Blood will be collected via an intravenous line at baseline and then 1, 2, 4, 6, 8, 10, 12 and 15 minutes after the first puff on the device. After the last sample is collected, the IV will be removed and participants will be asked to complete another CO measurement and to complete questionnaires about withdrawal and craving as well as questionnaires about their experience with the product.

	Time and Events Table									
	Baseline Phase	Switching Phase Follow-up Phase								
Study Week Number	0	1	2	3	4	5	6	10	10	10
Study Day	0	7	14	21	28	35	42	70	70	70
Study Visit Number	1	Ph #1	Ph #2	2	Ph #3	Ph #4	3	Ph #5	4 (ZOOM)	6
Measures/Questionnaires										
COVID screening questions (day prior to visit)	x			Х			х			
Screening Questions	x									
Daily Cigarette and E-cig Use Diary	x	х	x	х	X	Х	х			
Past 7 day Cig and E-cig use								X	Х	
Other Tobacco Use	X	X	Х	Х	X	Х	X	X		
E-cig Patterns of Use and Log		X	Х	Х	X	Х	X	X		
Concomitant medications	X	X	Х	Х	X	Х	X	X		
Medical History	x	ĺ								
Cigarette Details	x									
Adverse events	X	X	Х	Х	X	Х	Х	X		
Demographics (Including Social Determinants of Health (SDOH))	x									
Tobacco use history	x									
Importance/Confidence to Quit	Х			Х		ľ	X	X		
NIDA drug screener (past 3 months)	x									
Environmental tobacco smoke	x			X			X			
Cigarette/E-cig perceived health risk	x			X						
E-cig Perceived Benefits and Harms	x									
Cigarette and E-cig Liking and Evaluation scales	x			X			x	x		х
Study Product Side Effects questionnaire		x	x	X	x	Х	x	x		х
Cigarette dependence (HONC, FTND, PSCDI)	x			X			x	x		
E-cig Dependence (Penn State E-cig DI)				X			x	x		
Questionnaire smoking urges	X	X	Х	Х	X	Х	X	X		х
Minnesota withdrawal scale	X	Х	X	Х	X	Х	Х	X		х
Audit-C	x						X			
CES-D	X			Х			Х			
Kessler K6	Х			Х			X			
Perceived stress scale	X			Х			X			

				0.	00100000	510
Clinical COPD questionnaire (CCQ)	X	X	X			
PROMIS Sleep Disturbance & Impact	x	X	X			
Interheart and WI Prepare	X		X			
Real World E-cig Use				Х		
Interview					Х	
Biomeasures/Procedures						
Weight	X	X	X			
Height	X					
Exhaled CO	X	X	X			x
Blood pressure/pulse	X	X	X			
Pulmonary function test (FEV1, FVC, PEF, FEF25, FEF75, FEF25-75, FET)	x	x	x			
Urine sample (NNAL, CYMA, MHBMA3, 3HPMA,8- isoprostanes, creatinine, cotinine)	x	x	x			
Holter EKG test (10 minutes)	X		X			
Pregnancy test	x	X	X			
Product use procedure			1			v

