- **1.1.3** Aim 3: At the end of each participant's 6 week participation, they will be provided with information about the health effects of tobacco product use, how to purchase their own electronic cigarette and supplies if they wish to continue using one, and sources of assistance to quit smoking. They will then be asked to complete telephone and online survey four weeks later (10 weeks after switching).
 - 1.1.3.1 Our hypothesis is that participants randomized to nicotine-containing SRECs (as compared with those randomized to zero nicotine liquid) will be more likely to continue to try to abstain from cigarettes and to continue to use an e-cig at week 10 follow-up.

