7.4.4 Subject Compliance Monitoring

Participants will be given daily diaries to complete on which they will record the number of cigarettes smoked and number of e-cig puffs each day. Participants will be given detailed instructions on how to complete the logs. Questions will be asked at each contact to review participants' logs and to verify their daily conventional cigarette and e-cig use. Participants will also be asked to self-report their other tobacco use including products such as cigars, pipes, chew, snus, dip, hookah, and dissolvable tobacco. Exhaled carbon monoxide measurements and urine samples will be collected throughout the study to verify smoking intensity, nicotine, and cotinine levels.

Participants will be asked to return all of their used and unused study products and to bring their e-cigs to the study visits following randomization. At each of these visits, study staff will review the used pods to get an estimate of how much e-cig liquid was used by the participant.

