7.4.6.4 Return or Destruction of the Test Article

Participants will be dispose of their SREC device and all used and unused pods after completion of Phone Contact #5or if they are withdrawn. The devices provided to participants in this study are not commercially available and thus cannot be used without the pods provided in the study.

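### Aim 3's week-10 e-cig outcome can reach back into the supplied phase and can count leftover study pods

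*Combined protocol and SAP*

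**What the plan says.** Under Aim 3 (Section 1.1.3), participants finish six weeks, are told how to buy their own e-cig and where to find help to quit, and are then followed up: "They will then be asked to complete telephone and online survey four weeks later (10 weeks after switching". The hypothesis is that the nicotine arm "will be more likely to continue to try to abstain from cigarettes and to continue to use an e-cig at week 10 follow-up".

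Section 7.2.6 sets "Visit 3 (Day 42 -7/+14 days" and Section 7.2.7 sets "Phone Contact #5 (Day 70 ± 7 days". Both count from Visit 1 as Day 0 (Section 7.2.2), and neither refers to the actual date of the other.

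Two look-back periods apply at the call. Section 7.2.7 says that "past 7 day study product and cigarette use will be collected via a 7 day timeline follow-back (TLFB) procedure". Section 1.3 lists, among the week-10 outcomes, a count of e-cig days over the preceding 21 days.

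On supply, Section 7.2.6.2.4 has pods collected and reviewed at Visit 3, after which "Participants will then be able to retain some of the unused pods based on their usage". No number is given. Section 7.4.6.4 has participants "dispose of their SREC device and all used and unused pods after completion of Phone Contact" #5, or on withdrawal. It adds that the device is not sold commercially and does not work without the study's pods.

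Section 8.3 compares the two arms on the proportion still using an e-cig at week 10 by Fisher's exact test. It states neither a look-back period for that proportion nor any distinction by source of product.

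**The concern.** Aim 3 is about what participants do after free supply ends. Two features of the plan weaken the link between that question and what is recorded.

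The first is timing. The windows for Visit 3 and for the call vary independently, so the time since the end of the supplied phase differs between participants. If the call comes soon after Visit 3, a 21-day count includes days when the participant was still in the Switching Phase with study pods dispensed.

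The second is supply. Someone who reports e-cig use at week 10 may be finishing retained study pods or may have bought a product. The first is weak evidence of a choice to continue, while the second is what the purchasing information at Visit 3 leads up to. As planned, both count the same.

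At stake is the interpretation of one of the three specific aims. The primary endpoint, urinary NNAL at week 6, is not touched.

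**Working it through.** **Inputs**
- Visit 3 window: Day 42 -7/+14 (Section 7.2.6).
- Call window: Day 70 ± 7 (Section 7.2.7).
- Intended interval: four weeks (Section 1.1.3).
- Look-back periods: 21 days for e-cig days (Section 1.3); 7 days for the timeline follow-back (Section 7.2.7).

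**The plan's own figure.** Nominal gap = 70 - 42 = 28 days, which reproduces the stated four weeks.

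**Range the windows allow**
- Visit 3: 42 - 7 = 35 to 42 + 14 = 56.
- Call: 70 - 7 = 63 to 70 + 7 = 77.
- Minimum gap: 63 - 56 = 7 days.
- Maximum gap: 77 - 35 = 42 days.
- With every call exactly on Day 70: 70 - 56 = 14 to 70 - 35 = 35 days.

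**Overlap with the supplied phase.** Days of look-back before Visit 3 = look-back length minus gap, when positive.
- 21-day count: at most 21 - 7 = 14 days. There is overlap whenever the gap is under 21 days. For a call exactly on Day 70, that means a Visit 3 on Days 50 to 56 (70 - 50 = 20).
- 7-day follow-back: 7 - 7 = 0 at the minimum gap, so it never reaches before Visit 3.

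**How often.** The documents give no distribution of actual dates. Purely for illustration, assume that all 22 × 15 = 330 in-window pairs of days are equally likely.
- Gap under 21 days: a Visit 3 on Day 43 allows 1 such call day, Day 44 allows 2, and so on up to Day 56, which allows 14. The sum 1 + 2 + ... + 14 = 105, and 105/330 = 32%.
- Gap over 35 days: 7 + 6 + ... + 1 = 28, and 28/330 = 8%.
- Gap of 21 to 35 days: 330 - 105 - 28 = 197, and 197/330 = 60%.

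**Check of the remedy.** Require the call to be at least 21 days after Visit 3 and still within Days 63 to 77.
- Latest Visit 3: 56 + 21 = 77, the last permitted day, so the rule can always be met.
- Visit 3 on Day 42 or earlier: 42 + 21 = 63, so the full 15-day window remains.
- Visit 3 on Day 49: 49 + 21 = 70, so Days 70 to 77 remain.
- The gap then runs from 21 to 42 days, and overlap of the 21-day count is 21 - 21 = 0.

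**Supply.** No size can be computed, because the number of pods retained is not stated.

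**The case against.** The strongest reply is that week 10 is itself the intended time point. The Aim 3 sentence also says 10 weeks after switching, and Sections 1.3, 7.3 and 8.3 all use 10 weeks. Day 70 ± 7 implements that, and the two descriptions part only when Visit 3 is off Day 42. This stands, and it argues against moving the call to 28 ± 7 days after Visit 3. That would spread calls over Days 35 + 21 = 56 to 56 + 35 = 91, a 36-day span in place of the present 15. It also stands that 7 and 42 days are corner cases.

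Four stronger readings are tempting, and the documents do not support them.

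- *The variable gap biases the arm comparison.* Both windows apply to both arms alike, so timing alone blurs the outcome.
- *Leftover pods favour the nicotine arm.* Retention depends on usage, and usage may differ by arm, but heavier users might be allowed more pods or might have fewer unused ones left. Pods may also run out before the call, after which the device cannot be used. The direction is open.
- *The outcome should be self-obtained use only.* The hypothesis concerns continuing to use an e-cig, with no condition on source. Restricting it changes the estimand and would class someone still using only the study device as not continuing.
- *The pod rules contradict each other.* Section 7.4.4 says "Participants will be asked to return all of their used and unused study products" at visits, Section 7.2.6.2.4 lets some be kept after review, and Section 7.4.6.4 covers final disposal. These can largely be read in sequence, although the wording is loose.

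Finally, product source may already be captured. Section 7.2.7 asks about study product by name. The Time and Events Table lists a patterns-of-use log at this call and, as far as the broken table can be read, a form on real-world e-cig use. Their content is not visible, so a missing item cannot be asserted. What can be said is that Section 8.3 does not use source for Aim 3.

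**Conclusion.** The point holds as a matter of interpretation. The windows allow 7 to 42 days between Visit 3 and the call (nominal 28). At gaps under 21 days, the Section 1.3 count of e-cig days includes up to 14 days from before Visit 3. Week-10 e-cig use can also be leftover study product, and the Aim 3 analysis does not tell it apart from self-obtained use.

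The range follows directly from the stated windows. The 32% figure rests on an assumed uniform spread of dates and should not be read as a forecast. The overlap concerns the 21-day count. If the Section 8.3 proportion is derived from the 7-day follow-back, that proportion is free of overlap but still mixes product sources. Neither a bias between arms nor a direction for the effect of retained pods is shown.

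**What to change.** 1. **Timing.** Keep Day 70 ± 7 and add that the call takes place at least 21 days after the actual Visit 3. This preserves the week-10 anchor and keeps the 21-day count out of the supplied phase. The cost is a narrower scheduling window after a late Visit 3: 8 days if Visit 3 falls on Day 49, and Day 77 alone if it falls on Day 56.

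2. **Product source.** At Phone Contact #5, record whether e-cig use was of the study SREC or of a self-obtained product, using the existing e-cig forms if they already capture this. Keep any-source use as the stated Aim 3 outcome. Report self-obtained use by arm alongside it, together with the number of pods retained at Visit 3. The cost is at most one added response option and one added analysis.
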